#### Response:

All study personnel are active physicians or researchers at OCH and have been granted privileges by Kaleida Health IST to access the medical records in Powerchart for carrying out their duties as clinician or researchers. In addition, we are asking for a partial HIPAA waiver from our IRB for patient screening purposes.

# **17.0 Data Management and Analysis**

17.1 Describe the data analysis plan, including any statistical procedures. This section applies to both quantitative and qualitative analysis.

#### Response:

Univariate analysis will be used to determine if the subjects in each treatment arm differ at baseline through t-test or Wilcoxon Rank Sum testing for continuous data and Chi-square testing for categorical data. Any differences will be controlled for in the analysis of the primary outcome (length of acidosis) using linear regression. All outcomes will be correlated with the overall chloride load given via intravenous fluids during DKA management. All analyses will be performed using IBM SPSS software, version 25 (Chicago, IL) and SAS (SAS Institute Inc., Cary, NC) with significance set at p<0.05.

17.2 If applicable, provide a power analysis.

*NOTE:* This may not apply to certain types of studies, including chart/records reviews, survey studies, or observational studies. This question is asked to elicit

whether the investigator has an adequate sample size to achieve the study objectives and justify a conclusion.

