# **1.0 Objectives**

1.1 Describe the purpose, specific aims, or objectives of this research.

Response:

**Aim 1:** To compare the duration of acidosis after admission in children randomized to receive intravenous fluids containing normal saline (NS) to those receiving intravenous fluids containing lactated ringers (LR) during the treatment of diabetic ketoacidosis in the pediatric intensive care unit.

**Aim 2:** To correlate the duration of acidosis with the length of hospitalization and intensive care unit stay after admission in children randomized to receive intravenous fluids containing normal saline to those receiving intravenous fluids containing lactated ringers during the treatment of diabetic ketoacidosis in the pediatric intensive care unit.

1.2 State the hypotheses to be tested, if applicable.

*NOTE:* A hypothesis is a specific, testable prediction about what you expect to happen in your study that corresponds with your above listed objectives.

Response:

**Primary hypothesis:** Children with diabetic ketoacidosis (DKA) who are treated with intravenous fluids containing lactated ringers will have a shorter duration of metabolic acidosis after hospital admission than those treated with intravenous fluids containing normal saline.

**Secondary hypothesis:** The duration of acidosis after hospital admission in children with DKA will be positively associated with length of stay in the intensive care unit and hospital.

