# 2.0 Scientific Endpoints

2.1 Describe the scientific endpoint(s), the main result or occurrence under study.

*NOTE:* Scientific endpoints are outcomes defined before the study begins to determine whether the objectives of the study have been met and to draw conclusions from the data. Include primary and secondary endpoints. Some example endpoints are: reduction of

symptoms, improvement in quality of life, or survival. Your response should **not** be a date.

Response:

The **primary** study outcome will be the duration of metabolic acidosis after hospital admission.

Resolution of metabolic acidosis will be defined in three ways to delineate the iatrogenic effect from intravenous fluids from that of the primary pathology in diabetic ketoacidosis:

- 1. Serum ketone level <1mmol/L;
- 2. Venous pH > 7.3;
- 3. Serum bicarbonate level > 15mmol/L.

**Secondary outcomes**: Length of stay in the pediatric intensive care unit and length of stay in the hospital.

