DKA, the anion gap and ketosis have resolved, but acidosis persists due to an abnormally high chloride level caused by large volumes of NS coupled with the increased absorption of chloride by the kidney as less bicarbonate is generated due to the excretion of ketones in urine [8-10]. In retrospective data, the occurrence of HMA in DKA was correlated with a delayed resolution of acidosis and prolonged hospital stay. A prolonged hospital stay is associated with preventable financial burden, overutilization of health care resources, and missed days of work and school.

Lactated Ringers is an intravenous fluid that not only has lower chloride content than NS but also buffers acidosis by generating bicarbonate from lactate. By mitigating the rates of or severity of HMA, use of LR could potentially shorten length of stay and the morbidity of prolonged hospitalization.

There have been limited prospective clinical studies in pediatric patients examining the association of the chloride content of intravenous fluids and outcome in DKA. This prospective randomized controlled trial is being performed to compare the duration of acidosis and hospital length of stay in children with DKA who are admitted to a pediatric intensive care unit and are treated with intravenous fluids containing NS or LR. The primary study hypothesis is that use of LR will be associated with decreased duration of hyperchloremic metabolic acidosis and, therefore, shorter hospitalization than use of NS in the treatment of pediatric DKA.

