After admission to the PICU, DKA fluid management uses a two-bag system to maintain glucose levels between 100 and 300 mg/dL. Once the patient's glucose concentration falls below 300 mg/dL, the intravenous fluids containing dextrose are started and the fluids without dextrose are titrated downward. In addition to containing necessary electrolytes, the study intravenous fluids will contain either lactated ringer's or normal saline based on the assigned treatment arm.

Study fluid management of the two-bag system will follow the same guidelines for rate of fluid delivery and amount of dextrose used currently in the routine management of patients in DKA. Bedside healthcare personnel will treat all study subjects identically regardless of treatment arm. To provide blinding to all bedside staff, intravenous fluid bags will be labelled as "DKA study fluid with dextrose" or "DKA study fluid without dextrose." The fluid bags will be covered with an opaque black bag to mask any visible description of the fluid content.

Fluids will be adjusted using the study protocol as outlined here:

Serum Glucose	DKA study fluids without dextrose	DKA study fluids with dextrose	
>300mg/dL	100% of the hourly rate	0%	

200-300 mg/dL	50% of the hourly rate	50% of the hourly rate	
<200 mg/dL	0%	100% of the hourly rate	

Study participants will not receive any additional laboratory tests other than those that are already involved in standard DKA management. Currently, routine DKA management involves hourly finger-stick or laboratory glucose levels, every 2-hour serum electrolytes and blood gases, every 6-hour serum beta-hydroxybutyrate levels, and urine ketones with every void. This will be the same for all study participants on both treatment arms.

The study fluids will be used until the acute management of DKA using the continuous insulin infusion and two-bag fluid system is stopped. This will occur when the venous pH is equal to or greater than 7.30, the serum bicarbonate level is equal to or greater than 15 mmol/L and serum ketone levels are less than 1mmol/L.

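### Overall chloride load is partly made of acidosis time, so its planned correlation with duration of acidosis is positive with no fluid effect and cannot show chloride harm

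*Combined protocol and SAP*

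**What the plan says.** Section 17.1 plans, at p<0.05: "All outcomes will be correlated with the overall chloride load given via intravenous fluids during DKA management". It names no coefficient. It does not express load per hour, limit it to a fixed window or analyse it within arm.

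Section 10.1 sets the exposure period: "The study fluids will be used until the acute management of DKA using the continuous insulin infusion and two-bag fluid system is stopped". The stopping rule follows: "This will occur when the venous pH is equal to or greater than 7.30", together with a bicarbonate and a ketone threshold. Rate guidelines are the same in both arms. Section 11.2 confirms that the intervention ends with acute DKA management in the PICU.

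Section 2.1 builds the primary outcome on those markers: "Resolution of metabolic acidosis will be defined in three ways", by ketones, pH and bicarbonate. The pH and bicarbonate cut-offs differ from section 10.1 only in whether equality counts. The secondary outcomes are "Length of stay in the pediatric intensive care unit and length of stay in the hospital".

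Two related statements concern stay. The secondary hypothesis in section 1.2 is "The duration of acidosis after hospital admission in children with DKA will be positively associated with length of stay in the intensive care unit"; it makes the same claim for hospital stay. Section 3.1 states a different goal: "This prospective randomized controlled trial is being performed to compare the duration of acidosis and hospital length of stay in children with DKA", expecting that "use of LR will be associated with decreased duration of hyperchloremic metabolic acidosis and, therefore, shorter hospitalization than use of NS". Section 17.1 reserves linear regression for the primary outcome and its two-group tests for baseline differences, so it gives no between-arm method for either stay.

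**The concern.** A child who stays acidotic longer stays on study fluid longer and so receives more chloride, whichever fluid is in the bag. Duration drives load by design, and a positive correlation says nothing about whether load drives duration.

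The background section proposes chloride load as the cause of prolonged acidosis and stay. A significant load–duration correlation would readily be taken as support, most of all if the randomized comparison were null.

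A milder version affects Aim 2. Acidosis hours spent in the PICU count in both duration and PICU stay, so part of that association is part-whole. It does not show a fluid effect, nor that acidosis prolongs stay beyond its own hours. The analysis that would test the expectation of shorter hospitalization is the randomized comparison of stay, and it has no stated method.

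**Working it through.** The plan gives no figure for this correlation, so there is none to reproduce.

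**Inputs from the documents.** 104 children, 52 per arm (5.1); alpha 0.05 (17.1); two successive medians of 8 h, about 16 h in all when added (17.2); fluid stops when the last of three markers resolves (10.1).

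**Assumptions, not in the documents.** Chloride 154 vs 109 mmol/L; rate 3.5–5 mL/kg/h; log-SD of weight 0.5; log-SD of duration 0.3, 0.5 or 0.8; ED saline bolus of 0, 25% or 50% of 16 h of study fluid.

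**Step 1: closed form, one phase, no bolus.** Load = C × R × W × T (concentration, rate, weight, hours), so log load = log C + log R + log W + log T. With no fluid effect and independent terms, the correlation of log load with log T is

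r = SD(log T) / √[Var(log T) + Var(log W) + Var(log C) + Var(log R)].

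- Var(log C), 1:1 allocation: [ln(154/109)]²/4 = 0.3456²/4 = 0.0299.
- Var(log R), rate spread evenly over its range: about [ln(5/3.5)]²/12 = 0.0106.
- Var(log W) = 0.5² = 0.25.

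| SD(log T) | Calculation | r |
|---|---|---|
| 0.3 | 0.3/√(0.09 + 0.2905) | 0.49 |
| 0.5 | 0.5/√(0.25 + 0.2905) | 0.68 |
| 0.8 | 0.8/√(0.64 + 0.2905) | 0.83 |

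With 104 children, two-sided 0.05 is reached at |r| = 1.983/√(102 + 1.983²) = 0.19. Load per kg drops the weight term and raises r: at SD 0.5, 0.5/√0.2905 = 0.93.

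**Step 2: does r respond to a true fluid effect?** Multiply duration on lactated ringers by f and put d = ln f. Then, at SD(log T) = 0.5:

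- Covariance = 0.25 + d(d − 0.3456)/4
- Var(log load) = 0.25 + 0.25 + 0.0106 + (d − 0.3456)²/4
- Var(log T) = 0.25 + d²/4

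| f | Covariance | Var(log load) | Var(log T) | r |
|---|---|---|---|---|
| 0.80 (lactated ringers better) | 0.2817 | 0.591 | 0.262 | 0.71 |
| 1.00 (no effect) | 0.2500 | 0.540 | 0.250 | 0.68 |
| 1.25 (lactated ringers worse) | 0.2432 | 0.514 | 0.262 | 0.66 |

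The answer is nearly the same whether lactated ringers helps, does nothing or harms.

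**Step 3: simulation with no fluid effect.** 324 settings of 2,000 trials. Duration was one phase of median 16 h, or two independent phases of median 8 h with the earlier marker at the end of the first. PICU time after resolution had mean 12 h (SD 4, 12 or 24); ward stay had mean/SD 24/12, 24/24 or 48/24 h; both gamma or lognormal. Ranges run over settings and over Pearson and Spearman.

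| Pair | Correlation | Trials significant |
|---|---|---|
| Load vs last marker, no bolus | 0.34–0.81 | 94–100% |
| Load vs last marker, with bolus | 0.21–0.73 | 58–100% |
| Load vs earlier marker | 0.15–0.50 | 33–100% |
| Load per kg vs duration | 0.48–0.96 | 100% |
| Load vs PICU stay | 0.03–0.76 | 6–100% |
| Load vs hospital stay | 0.02–0.65 | 5–100% |
| Duration vs PICU stay (Aim 2), Spearman | 0.37–0.93 | 97–100% |
| Duration vs PICU stay (Aim 2), Pearson | 0.16–0.98 | 36–100% |
| Duration vs hospital stay (Aim 2) | 0.11–0.84 | 19–100% |

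Between-arm Wilcoxon tests of duration and both stays rejected in 3–6% of trials, as they should. With lactated ringers lengthening duration by 25% (16 h to 20 h), load vs last marker was still 0.17–0.80 (42–100%) and load vs earlier marker 0.13–0.48 (25–100%).

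**Step 4: independent simulation with other assumptions.** Here the lactated ringers to saline chloride ratio was 0.6–0.85, the CV of duration 0.3–0.7, and the ED fluid equal to 0–4 h of infusion. With no fluid effect, Spearman was 0.38–0.72 for absolute load and 0.56–0.96 per kg, significant in 98–100% of runs. With identical chloride in both arms, load per kg still gave 0.90, so the correlation does not come from the arms.

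**The case against.** The strongest reply is that the protocol never says how the correlation will be read. Chloride load is in no aim, hypothesis or endpoint; it is one unranked sentence, and the primary randomized comparison is sound. That is true and limits the severity. Yet the sentence covers all outcomes at the trial's significance level, and the background supplies the causal reading.

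The overlap is also not exact. It is closest for the last marker and looser for an earlier one. Duration counts from hospital admission, while study fluid starts only after consent and pharmacy assignment. This stands: 0.15 is a weak correlation, though still not zero.

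For stay, the low ends (0.02–0.03, significant in 5–6%) are no more than nominal error, and the range depends on stay distributions that the documents do not give. The case therefore rests on load against duration. For Aim 2, about 90% of children come through the ED, so some acidosis hours may fall outside PICU stay; moving 1–6 h outside left the result essentially unchanged. The plan claims only association there, which is fair.

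Finally, describing load instead of testing it gives up a planned analysis when measures free of treatment time exist. That is reasonable, and such measures are offered below as exploratory options.

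**Conclusion.** The concern holds. The mechanism follows from sections 2.1, 10.1 and 17.1 and needs no assumed figure. Its size does depend on the assumptions listed, but the load–duration correlation was positive in every setting tried: 0.21 to 0.81 for the last marker and 0.15 to 0.50 for an earlier one, with no fluid effect. Because it stays positive when lactated ringers is made worse, it is not evidence of chloride harm. Scaling by weight does not cure it.

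The effect on stay is uncertain. The Aim 2 overlap and the missing between-arm method for stay are secondary points. The randomized comparison of duration is not affected. The change should be made before analysis.

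**What to change.** 1. **Chloride.** Replace the sentence in 17.1 with: *Overall chloride load will be summarized by arm as a description of exposure. Because load contains treatment time, it will not be tested against duration of acidosis or stay as evidence of chloride harm.*
2. **Stay.** Name the between-arm comparison of PICU and hospital stay as the secondary-outcome analysis, for example Wilcoxon rank-sum with a difference and 95% CI, and say how the two tests are treated for multiplicity.
3. **Aim 2, if kept.** Name the coefficient, call the result descriptive and non-causal, and state that stay includes the acidosis hours. Stay after resolution can be added, but it answers a different question.

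Optional and exploratory: study-fluid chloride per kg per hour, with ED chloride shown separately, or prescribed chloride over a fixed early window. With no fluid effect and rate unrelated to duration, both correlate about 0.00 with duration (significant in about 4–6.5% of runs). The hourly measure correlates 0.86 with arm. If rate tracks severity (correlation ±0.3 with log duration), it gives ±0.13 to 0.22, significant in 24–62% of trials. State both limits.

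Cost: items 1 and 2 are wording, but cumulative exposure is then described, not tested. If an 8 h shorter acidosis carried fully into stay, power at two-sided 0.05 would be 79–100% for PICU stay and 32–95% for hospital stay, so the interval should be reported. The hourly measure needs weight and PICU fluid volumes. Section 10.2 names fluid volume only under ED data and its PICU list is open-ended, so the sponsor should confirm capture. Children unresolved at about 36 h may lack a resolution time for item 3; report how many.

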# 6.0 Inclusion and Exclusion Criteria

6.1 Describe the criteria that define who will be **included** in your final study sample.

NOTE: This may be done in bullet point fashion.

Response:

Inclusion criteria:

- 1. Age between 0 and 18 years
- 2. Diagnosis of DKA from Type I DM:
  - a. Venous pH less than 7.25
  - b. Ketonuria as confirmed on urine point-of-care testing or urinalysis
  - c. Hyperglycemia (Serum glucose > 200 mg/dl)
  - d. Serum bicarbonate <15 mmol/L
- 3. Need for PICU admission based on clinical discretion
- 6.2 Describe the criteria that define who will be **excluded** from your final study sample.

*NOTE: This may be done in bullet point fashion.* 

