#### Response:

Baseline demographic data that will be collected including age, sex, race, comorbid conditions, vital signs, number of hospitalizations for DKA in the preceding 12 months, and date and time of transfer to the PICU.

ED lab data that will be collected include all laboratories obtained in the ED, intravenous fluid volume and type administered, time to start of insulin and PRISM score.

PICU lab data that will be collected include all pH, bicarbonate, anion gap, chloride and beta-hydroxybutyrate levels, sodium, potassium, BUN, creatinine, glucose etc. If the patient remains in DKA after 32 hours after initial ED labs, PICU lab data will be collected until the closest to 36 hours after the initial ED labs were obtained.

Outcomes to be collected include length of stay in the hospital and ICU, resolution of acidosis including time to a serum pH>7.30, bicarbonate >15mg/dl, and normal anion gap.

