# Response:

Please find the attached (1) Demographic data form, (2) ER laboratory data form, (3) Outcomes data form, (4) PICU laboratory data form, (5) Screening form

10.4 Describe any source records that will be used to collect data about subjects (e.g. school records, electronic medical records).

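### The planned chloride-load correlations use a total load with no allowance for body size in children aged 0 to 18, and need size scaling together with a fixed early window or a rate

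*Combined protocol and SAP*

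**What the plan says.** Section 17.1 sets out the exposure analysis in one sentence: "All outcomes will be correlated with the overall chloride load given via intravenous fluids during DKA management". It states no scaling, covariate, time window or type of correlation. The only adjustment in that section is for baseline differences between arms: "Any differences will be controlled for in the analysis of the primary outcome (length of acidosis) using linear regression". That applies to the primary outcome and not to the chloride correlations.

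The age criterion in Section 6.1 is "Age between 0 and 18 years". Section 10.2 gives the baseline data as "including age, sex, race, comorbid conditions, vital signs, number of hospitalizations for DKA" in the previous year, plus the date and time of PICU transfer; weight is not named. Fluid data appear under the ED heading only: "intravenous fluid volume and type administered, time to start of insulin and PRISM score". The PICU list names laboratory values.

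Section 10.1 expresses fluids as percentages of an hourly rate and prints no formula for that rate. On duration it says: "The study fluids will be used until the acute management of DKA using the continuous insulin infusion and two-bag fluid system is stopped". It ties that stop to pH, bicarbonate and ketone thresholds, nearly the same as those that define resolution of acidosis in Section 2.1.

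**The concern.** Hourly fluid rates for an infant and an 18-year-old presumably differ several-fold because of size. Two children with the same chloride exposure per kg can then have very different total loads. Two consequences follow.

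- If size is unrelated to the outcome, its variation is noise in the exposure and pulls a real association towards zero.
- If size or age is related to duration of acidosis or to stay, the correlation is confounded, in either direction.

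The adjustment in Section 17.1 does not help. Weight can be balanced between arms and still drive a correlation pooled over all children.

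The background in Section 3.1 rests on chloride exposure, so readers will look to this analysis for a dose relation. As planned, a null result could be dilution and a positive one could be confounding. A positive result could also arise only because children with longer acidosis received fluid for longer.

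**Working it through.** The plan gives no figure for this analysis, so there is none to reproduce. It gives no weights, fluid volumes, rate formula or chloride concentrations either, so the inputs below other than the sample size are assumptions, and results are shown as ranges.

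**Inputs**
- Sample size 104, 52 per arm (Sections 5.1 and 17.2).
- Chloride 154 against 109 mmol/L (assumed).
- SD of log weight, s: 0.45 or 0.60 (assumed).
- Volume proportional to weight^b, with b = 0.65 or 1 (assumed).
- SD of log size-adjusted load within arm: 0.25 or 0.40 (assumed).
- SD of log infusion duration: 0.4 or 0.8, unrelated to weight, with no chloride effect on it (assumed).

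**Variance components of log load**
- Arm: A = (ln(154/109)/2)² = (0.3456/2)² = 0.0299.
- Size: S = b²s², from 0.65² × 0.45² = 0.0856 to 1² × 0.60² = 0.36.
- Within arm: E = 0.0625 or 0.16.
- Duration: T = 0.16 or 0.64.

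**Step 1: share due to size, fixed window.** Share = S/(S + A + E).
- Lowest: 0.0856/(0.0856 + 0.0299 + 0.16) = 0.31.
- Highest: 0.36/(0.36 + 0.0299 + 0.0625) = 0.80.

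**Step 2: share due to size, load accumulated until fluids stop.** Share = S/(S + A + E + T).
- Lowest: 0.0856/(0.2755 + 0.64) = 0.09.
- Highest: 0.36/(0.4524 + 0.16) = 0.59.

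In the lowest case duration takes 0.64/0.9155 = 70% of the variance, so size is not always the largest part.

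**Step 3: dilution, fixed window.** If size is unrelated to outcome, a correlation r with size-adjusted load becomes r × √(1 − share). With r = 0.30:
- 0.30 × √(1 − 0.311) = 0.249.
- 0.30 × √(1 − 0.796) = 0.136.

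Power by the Fisher approximation is Φ(atanh(r) × √101 − 1.96), taking the 0.05 level of Section 17.1 as two-sided (sidedness is not stated):
- r = 0.30: Φ(3.11 − 1.96) = 88%.
- r = 0.249: Φ(2.56 − 1.96) = 72%.
- r = 0.136: Φ(1.37 − 1.96) = 28%.

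**Step 4: confounding, fixed window.** Suppose weight and duration correlate at 0.2 and chloride has no effect. Unscaled load then shows a spurious correlation of 0.2 × √share, from 0.2 × √0.311 = 0.11 to 0.2 × √0.796 = 0.18. Per-kg scaling brings it to 0 when b = 1. When b = 0.65 it over-corrects: the leftover size variance is 0.35²s², at most 0.0441, and the correlation reaches −0.2 × √(0.0441/(0.0441 + 0.0299 + 0.0625)) = −0.11. Weight or age is therefore also needed in the model.

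**Step 5: the mechanical link, load accumulated until fluids stop.** With no chloride effect at all, the correlation of log load with log duration is √(T/(S + A + E + T)).
- Lowest: √(0.16/(0.36 + 0.0299 + 0.16 + 0.16)) = 0.47.
- Highest: √(0.64/(0.0856 + 0.0299 + 0.0625 + 0.64)) = 0.88.

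With size removed (per kg, with weight in the model), S drops out.
- Lowest: √(0.16/(0.0299 + 0.16 + 0.16)) = 0.68.
- Highest: √(0.64/(0.0299 + 0.0625 + 0.64)) = 0.93.

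Scaling a cumulative load makes the artefact stronger, from 0.47-0.88 to 0.68-0.93.

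**The case against.** The chloride correlation is one sentence. It is not an aim, hypothesis or endpoint in Sections 1 and 2, and the power statement in Section 17.2 does not cover it. The word overall may simply mean summed over the ED and the PICU. Apart from the sample size, every input to the calculation is assumed. Section 10.2 lists categories rather than every field, age is collected, and all data come from the electronic record (Section 10.4). Scaling alone would also strengthen a spurious result.

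Much of this stands. It limits the point to a supportive analysis and shapes the remedy. It does not make an unscaled load suitable: even if the word means only ED plus PICU, nothing in the plan tells the analyst to allow for size.

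Three stronger readings are tempting but not supported.
- *That the correlations largely measure how big the child is.* Size takes anywhere from 9% to 80% of the variance of log load, depending on the window and the assumptions. It enters the correlation with outcome as a signal only if size predicts outcome, and the documents do not say that it does.
- *That load cannot be scaled because weight is not collected.* Weight is not named in Section 10.2, but the demographic form listed in Section 10.3 is not shown and may contain it.
- *That this is the trial's only mechanistic analysis.* Section 2.1 uses three definitions of resolution to separate the effect of the fluids from that of the disease, and Section 10.2 collects serial chloride, anion gap and beta-hydroxybutyrate.

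**Conclusion.** The point holds for a supportive analysis and should be corrected. Section 17.1 pools an unscaled total load over ages 0 to 18 with no adjustment for size. Size is then a substantial, though not always the largest, source of variation in the exposure, and it dilutes a real association or confounds it. The mechanical link between cumulative load and duration has to be dealt with at the same time, since correcting size alone would make a chloride effect look stronger when none exists.

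The direction of these effects follows from the text plus one assumption, that fluid rates rise with body size. The sizes rest on the assumed spread of weight, rate and duration, and actual chart data would narrow them. The randomised comparison of duration of acidosis between arms does not use chloride load and is unaffected.

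**What to change.** In Section 17.1, replace the overall load with one of two definitions, chosen before unblinding:
- chloride per kg body weight (mmol/kg) over a fixed early window, short enough that few children have already come off study fluids; or
- a rate in mmol/kg/h.

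Fit it in a model with weight or age and treatment arm. Weight or age covers the case where fluid per kg falls with size. Arm separates the randomised contrast from non-randomised variation in load. Name the method and label the analysis supportive.

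In Section 10.2, name admission weight and PICU fluid volume and type. Without the PICU fluids, the overall load cannot be computed from the listed items.

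The cost is two or three more chart fields and one derived variable, with no new procedure or patients. The drawback is that a fixed window ignores chloride given later.
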